8.2.3 Special Diet or Activities

Not applicable

8.3 **Examination Procedures**

8.3.1 Procedures to be Performed at the Study Visit with Regard to Trial Objective(s)

Visit 1 (Day -14 -16/+2, screening, vehicle CAE)

- Informed consent and HIPAA
- Demographics (e.g., gender, date of birth, race, ethnicity)
- Medical/medication & ocular history
- Urine pregnancy test (as needed)
- Subject-reported ocular discomfort (0-100 VAS)
- Visual acuity (ETDRS)
- Slit lamp examination
- Fluorescein staining
- Inclusion/exclusion criteria review
- In-office vehicle instillation by trained site staff (approximately 5 minutes prior to CAE entry)
- CAE exposure (100 minutes, vehicle administration at approximately 50 minutes) with subject-reported ocular discomfort collected at 10, 15, 20, 25, 30, 35, 40, 45, 65, 70, 75, 80, 85, 90, 95, and 100 minutes in the CAE
- CAE exit
- Slit lamp examination
- Intraocular pressure
- Schedule for Visit 2

Visit 2 (Day 1, randomization, QID test article administration)

- Medical/medication update
- Adverse event query
- Visual acuity (ETDRS)
- Slit lamp examination
- Subject-reported ocular discomfort prior to randomization (0-100 VAS)
- Inclusion/exclusion criteria review
- Randomization/enrollment
- In-office Dose #1

- In-office Dose # 2
[REDACTED]
- In-office Dose #3
[REDACTED]
- In-office Dose #4
- Subjects will return to clinic the following day

Visit 3 (Day 2, test article CAE, trial exit)

- Medical/medication update
- Adverse event query
- Urine pregnancy test (as needed)
- Visual acuity (ETDRS)
- Slit lamp examination
- Subject-reported ocular discomfort (0-100 VAS)
- In-office test article instillation by trained site staff (approximately 5 minutes prior to CAE entry)
- CAE exposure (100 minutes, test article administration at approximately 50 minutes) with subject-reported ocular discomfort collected at 10, 15, 20, 25, 30, 35, 40, 45, 65, 70, 75, 80, 85, 90, 95, and 100 minutes in the CAE
- CAE exit
- Slit lamp examination
- Intraocular pressure
- Trial exit

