10.9 Safety Variables

Adverse events will be coded using the MedDRA dictionary.

Frequencies and percentages will be provided per treatment arm of subjects with treatment-emergent adverse events (TEAEs), serious TEAEs, and TEAEs causing premature discontinuation. An adverse event is treatment-emergent if the adverse event occurs or worsens after the first dose of randomized treatment. Furthermore, frequencies will be given of subjects with TEAEs by system organ class, by system organ class and preferred term, by system organ class, preferred term and maximal severity, by system organ class, preferred term and strongest relationship, and by system organ class, preferred term, maximal severity, and strongest relationship. Separate analyses will be performed for ocular specific and all adverse events (including systemic).

Other safety endpoints, including visual acuity, slit lamp examination, and intraocular pressure, will be summarized by treatment arm and visit using descriptive statistics. Changes or shifts from baseline will also be summarized where appropriate. For assessments performed by eye, eyes will be summarized separately.

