17.1 Adverse Events

An adverse event is defined as any untoward medical occurrence associated with the use of an test article in humans, whether or not considered test-article-related. An adverse event can be any unfavorable and unintended sign (e.g., an abnormal laboratory finding), symptom, or disease temporally associated with the use of test article, without any judgment about causality. Exacerbation of conditions related to the signs and symptoms of dry eye disease will not be reported as an adverse event. The adverse event reporting period ends upon trial exit. Study drug includes the investigational drug under evaluation.

All adverse events will be coded using MedDRA Version 27.0 (or higher).

Treatment-emergent adverse events (TEAEs) are defined as any adverse event that occurs or worsens on or after the first dose of study treatment. Adverse events recorded in the eCRF which began prior to treatment will not be included in the summary tables but will be included in the adverse event data listings.

An overall summary will be presented that includes the number and percentage of subjects who experienced at least one AEs, ocular AEs, non-ocular AEs, SAEs, AEs by maximal severity, AEs by relationship to study procedure, AEs leading to treatment discontinuation, and AEs resulting in death by treatment arm for the Safety Population. In addition, overall TEAEs and the number and percentage of subjects who experienced at least one TEAE, ocular TEAEs, non-ocular TEAEs, TE-SAEs, TEAEs by maximal severity, TEAEs by relationship to study procedure, TEAEs leading to treatment discontinuation, and TEAEs resulting in death by treatment arm for the Safety Population.

Separate summaries will be provided for the following categories of AEs:

- Ocular AEs by SOC and PT
- Non-ocular AEs by SOC and PT

- Ocular TEAEs by SOC and PT
- Non-ocular TEAEs by SOC and PT
- Instillation Site Ocular TEAEs by Duration of Time
- Ocular TEAEs by SOC, PT, and maximal severity
- Non-ocular TEAEs by SOC, PT, and maximal severity
- Ocular TEAEs by SOC, PT, and strongest relationship to study procedure
- Non-ocular TEAEs by SOC, PT, and strongest relationship to study procedure
- Ocular TEAEs by SOC, PT, maximal severity, and strongest relationship to study procedure
- Non-ocular TEAEs by SOC, PT, maximal severity, and strongest relationship to study procedure
- TEAEs That Led to Premature Treatment Discontinuation
- SAEs

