Adverse Events and TEAEs will be summarized using discrete summary statistics and presented by treatment arm and all subjects for the the Safety Population. If a subject reports the same PT multiple times within the same SOC, that PT will only be reported once within that SOC. As with the PT, if a subject reports multiple conditions within the same SOC, that SOC will only be reported once. In the summaries, SOCs will be listed in ascending alphabetical order. PTs will be listed in order of descending frequency within each SOC for all subjects.

A missing severity will be considered Severe. 'Drug Related' will be defined as 'Definitely Related', 'Probably related' or 'Possibly Related', excluding 'Unlikely Related' and 'Not Related'. A missing relationship will be considered as 'Definitely Related'.

All AEs, ocular AEs, non-ocular AEs, and SAEs will be presented in subject listings.

18. Other Safety Variables

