18.3 Intraocular Pressure

Intraocular pressure will be measured in each eye by contact tonometry by the examiner and the results will be recorded in mmHg. Intraocular pressure will be performed post--CAE exposure. A single measurement is made to obtain a determination of intraocular pressure. The same tonometer employing the investigator's standard technique will be used throughout the trial. In addition, all reasonable efforts will be made to have the same examiner obtain all intraocular pressure measurements for a given subject.

The Intraocular pressure values and changes from baseline for OD and OS, separately, will be summarized using continuous descriptive statistics by visit and eye for each treatment condition and for all actively treated subjects. A subject listing of intraocular pressure also will be produced.

19. Additional Analyses

Additional analyses for the purpose of sensitivity assessment, hypothesis generation, and improved understanding of the treatment effect be conducted as ad-hoc analyses. All ad-hoc analyses will be identified in the CSR.

Sensitivity analyses for the primary analysis will include the following:

- A MMRM with Visit 3 ocular discomfort score as the dependent variable (compared at the same time points specified for the primary endpoint analysis [80 min to 100 min]); the Visit 3 baseline (pre-Dose 1 at Visit 2), the year of dry eye disease diagnosis (e.g., 1997), the time point-matched Visit 1 scores, and the average and standard deviation of all ocular discomfort scores from Visit 1 as covariates; and time (10 min to 100 min), treatment arm, and month of Visit 1 as factors, with correlated errors due to eye and time point; and

- Observed data only using the PP population.

Additional sensitivity analyses with time point removed from the primary model may be run by time point.

20. Revision History

Documentation of revision to the SAP will commence after approval of the Final version 1.0.

21. Reporting Conventions

The following reporting conventions will be adopted for the presentation of trial data. These conventions will enhance the review process and help to standardize presentation with common notations.

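### SAP 17.1 counts worsening events as treatment-emergent, then excludes events that began before treatment from its summary tables, with no exception for worsening and no limit to the TEAE tables

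*SAP*

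**What the plan says.** SAP 17.1 defines a TEAE as "any adverse event that occurs or worsens on or after the first dose of study treatment". The sentence after it reads "Adverse events recorded in the eCRF which began prior to treatment will not be included in the summary tables", and sends those events to the listings.

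The same section then orders two kinds of output. The overall summary starts with subjects who "experienced at least one AEs, ocular AEs, non-ocular AEs, SAEs, AEs by maximal severity" and continues through relationship, discontinuation and death, before repeating these categories for TEAEs. The list of separate summaries opens with "Ocular AEs by SOC and PT" and its non-ocular counterpart, then gives the TEAE versions, and ends with SAEs. Later, 17.1 confirms that both sets are tabulated: "Adverse Events and TEAEs will be summarized using discrete summary statistics and presented by treatment arm".

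Protocol 10.9 has its own definition: "An adverse event is treatment-emergent if the adverse event occurs or worsens after the first dose of randomized treatment". It has no exclusion sentence. Protocol 9.1 starts adverse event collection at consent and treats the worsening of a pre-existing medical condition during the trial as a new adverse event.

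**The concern.** Two adjacent sentences can classify the same event differently. An event that began in the run-in and worsened after the first randomized dose is a TEAE under the definition, yet under the next sentence it has no place in any summary table. The exclusion also refers to summary tables in general, and that term covers the all-event tables ordered a few lines below.

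Run-in events are collected by design. Consent, two vehicle doses and a 100-minute CAE exposure all take place at Visit 1. In Protocol 8.3.1 the Visit 2 adverse event query is listed ahead of "In-office Dose #1". At stake is whether the by-arm safety tables follow the definition or the exclusion. That choice should be fixed in the text before unmasking, and not left to whoever programs the tables.

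**Working it through.** No figure in the plan is in dispute, so the check compares the rules and counts the tables they reach.

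**Sets.** Take the reference dose as the first randomized dose on Day 1 (Protocol 10.9). Let A be events that begin on or after it, B events that begin before it, and W the part of B that worsens on or after it.

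- SAP definition of a TEAE: A + W.
- All-event tables, as their titles imply: A + B.
- Exclusion sentence: remove B, which leaves A.

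**Results under each reading.**

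| Scope of the exclusion | How worsening is recorded | TEAE tables | All-event tables |
|---|---|---|---|
| All summary tables | Original onset kept | A (W lost) | A (B lost) |
| All summary tables | New event, new onset | A, agrees with the definition | A (original run-in records lost) |
| TEAE tables only | Original onset kept | A (W lost) | A + B |
| TEAE tables only | New event, new onset | A, agrees with the definition | A + B |

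With a new onset date, W moves into A, so the TEAE tables agree with the definition. Only the last row has no conflict. Its two conditions are that the sentence is confined to TEAE tables, which 17.1 does not say, and that worsening gets its own onset date, which Protocol 9.1 supports for pre-existing conditions but 17.1 does not repeat.

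**Tables reached if the scope is all summary tables.**

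- Separate summaries in 17.1: 13 listed, 10 restricted to TEAEs, 13 − 10 = 3 not restricted (ocular AEs, non-ocular AEs, SAEs).
- Overall summary categories not restricted to TEAEs: any AE, ocular, non-ocular, SAEs, maximal severity, relationship, leading to discontinuation, death = 8. Each has a TEAE counterpart.
- The ocular and non-ocular AE tables by SOC and PT would then hold the same set A as their TEAE versions.

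**Can B contain events?** The protocol's Visit 1 window is Day −14, −16/+2, that is Day −30 to Day −12. With no Day 0 (SAP 5.1), Visit 1 falls 12 to 30 days before Day 1. Collection runs throughout that time, and one of the two scheduled adverse event queries (Visit 2, not Visit 3) is listed before the first randomized dose. So B need not be empty, but the documents give no event rate from which to estimate its size.

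**Scale.** Protocol section 4 plans about 55 subjects per arm, so one subject is 1/55 = 1.8 percentage points. This is the weight of one subject and does not estimate an effect.

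**The case against.** The strongest reply has four parts.

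- **Worsening is largely covered.** Protocol 9.1 makes a worsened pre-existing condition a new adverse event and asks for a date of onset. Recorded that way, it begins after dosing and the exclusion does not reach it. SAP section 2 regards its analyses as compatible with the protocol, and 17.1 does not revoke this rule. SAP 17.1 also keeps dry eye exacerbations out of adverse event reporting. This removes much of the problem. What stands is the narrower case in which a site leaves the worsening under the original record, or does not regard an event that arose after consent as a pre-existing condition. The case report form is not available to settle how often that could happen.
- **Context favours TEAE tables only.** The sentence directly follows the TEAE definition, and the all-event tables would have little purpose otherwise. This is probably the intent. It would preserve the all-event and SAE tables but would still drop W where the original onset date is kept.
- **The result depends on the reference dose.** If treatment meant the Visit 1 vehicle, the sentence would remove only events between consent and that dose, and most run-in events would stay in the tables. SAP 5.1 labels Visit 1 a vehicle treatment visit and SAP 15.2 counts exposure from Visit 1. However, Protocol 10.9 names randomized treatment, and SAP 19 fits it by placing "the Visit 3 baseline (pre-Dose 1 at Visit 2"). The loss of run-in events is therefore conditional on the Day 1 reference.
- **Little is lost for comparing the arms.** Run-in events that did not worsen arose before randomization and say nothing about reproxalap against vehicle. This is correct, and it keeps the point minor.

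A reader might infer more: that the plan certainly miscounts worsening events, that it withholds run-in SAEs from the report, or that the TEAE reference dose is undefined. The documents do not support these. Protocol 9.1 limits the first. For the second, 17.1 puts all adverse events and SAEs in subject listings, and the sentence was probably not aimed at the SAE table. For the third, Protocol 10.9 supplies the reference dose, so the SAP's looser term needs aligning but is not a separate defect.

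**Conclusion.** The point holds as a minor inconsistency in SAP 17.1. The exclusion sentence conflicts with the definition before it because it has no exception for worsening, and as worded it reaches all-event and SAE tables that the same section orders. The conflict over worsening assumes the Day 1 reference dose and an event kept under its original onset date. The loss from 3 of 13 separate summaries and 8 overall-summary categories assumes the Day 1 reference dose and the literal scope, which is probably not what was meant.

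The number of subjects affected is unknown and probably small, and the direction of any difference between arms cannot be stated. Only descriptive safety counts are involved. The listings keep every event, and the efficacy analysis is untouched.

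**What to change.** Before database lock, make two edits in SAP 17.1.

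1. Replace the exclusion sentence with: *Adverse events that began before the first dose of randomized treatment and did not worsen on or after it are excluded from the TEAE tables; they are included in the all-AE tables, the SAE table and the listings.*
2. In the TEAE definition, change study treatment to randomized treatment, to match Protocol 10.9.

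Two further alignments are optional: repeat the Protocol 9.1 rule, so that worsening after dosing is recorded as a new event with its own onset date; and state in SAP 9.3 which first dose date applies when adverse event dates are imputed.

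The cost is two changed sentences and no new assessments. Any record in which a site kept worsening under the original entry would need a data query; the number is unknown and probably small.

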18.1 Visual Acuity (ETDRS)

Visual acuity will be performed pre-CAE (and pre symptom assessment) and again at post-CAE exposure. The logarithm of the minimum angle of resolution (logMAR) visual acuity must be assessed using an ETDRS chart. The procedure used will be consistent with the recommendations provided for using the ETDRS eye chart. Subjects should use their most recent correction to attain their best-corrected visual acuity.

The observed and change from baseline visual acuity will be summarized for OD and OS, separately. Continuous descriptive statistics by visit for each treatment condition will be presented. A subject listing of visual acuity will also be produced.

18.2 Slit Lamp Biomicroscopy Examination

A slit lamp biomicroscopy examination of the cornea, conjunctiva, anterior chamber, iris, lens, and lid will be performed pre-CAE (and pre symptom assessment) and again at post-CAE exposure. The results will be graded as normal, Abnormal Not Clinically Significant (NCS) or Abnormal Clinically Significant (CS). Abnormal findings will be described.

The results will be summarized using counts and percentages for each treatment condition at each visit for OD and OS, separately. Percentages will be based on the number of subjects in each treatment condition with responses. Shift tables for the slit lamp biomicroscopy parameters will also be provided comparing each follow-up visit to baseline. A subject listing of the slit lamp biomicroscopy parameters will also be produced.

18.3 Intraocular Pressure

Intraocular pressure will be measured in each eye by contact tonometry by the examiner and the results will be recorded in mmHg. Intraocular pressure will be performed post--CAE exposure. A single measurement is made to obtain a determination of intraocular pressure. The same tonometer employing the investigator's standard technique will be used throughout the trial. In addition, all reasonable efforts will be made to have the same examiner obtain all intraocular pressure measurements for a given subject.

The Intraocular pressure values and changes from baseline for OD and OS, separately, will be summarized using continuous descriptive statistics by visit and eye for each treatment condition and for all actively treated subjects. A subject listing of intraocular pressure also will be produced.

19. Additional Analyses

Additional analyses for the purpose of sensitivity assessment, hypothesis generation, and improved understanding of the treatment effect be conducted as ad-hoc analyses. All ad-hoc analyses will be identified in the CSR.

Sensitivity analyses for the primary analysis will include the following:

- A MMRM with Visit 3 ocular discomfort score as the dependent variable (compared at the same time points specified for the primary endpoint analysis [80 min to 100 min]); the Visit 3 baseline (pre-Dose 1 at Visit 2), the year of dry eye disease diagnosis (e.g., 1997), the time point-matched Visit 1 scores, and the average and standard deviation of all ocular discomfort scores from Visit 1 as covariates; and time (10 min to 100 min), treatment arm, and month of Visit 1 as factors, with correlated errors due to eye and time point; and

- Observed data only using the PP population.

Additional sensitivity analyses with time point removed from the primary model may be run by time point.

20. Revision History

Documentation of revision to the SAP will commence after approval of the Final version 1.0.

21. Reporting Conventions

The following reporting conventions will be adopted for the presentation of trial data. These conventions will enhance the review process and help to standardize presentation with common notations.

21.1 General Reporting Conventions

- All tables and data listings will be developed in Landscape Orientation, unless presented as part of the text in a CSR.
- Figures will be presented in Landscape Orientation, unless presented as part of the text in a CSR.
- Legends will be used for all figures with more than one variable or item displayed.
- Figures will be presented in color with treatment condition distinguished by different symbols and colors. Lines in figures should be wide enough to view the line after being photocopied.
- Specialized text styles, such as bolding, italics, borders, shading, superscripted and subscripted text will not be used in tables, figures, and data listings unless they add significant value to the table, figure, or data listing.
- Only standard keyboard characters should be used in tables and data listings. Special characters, such as non-printable control characters, printer specific, or font specific characters, will not be used on a table, figure, or data listing. Hexadecimal character representations are allowed (e.g., μ , α , β).
- All titles will be centered on a page. The ICH numbering convention is to be used for all tables, figures, and data listings.
- All footnotes will be left justified and the bottom of a page. Footnotes must be present on the page where they are first referenced. Footnotes should be used sparingly and must add value to the table, figure, or data listing. If more than four footnote lines are planned, then a cover page may be used to display footnotes.

- Missing values for both numeric and character variables will be presented as blanks in a table or data listing. A zero (0) may be used if appropriate to identify when the frequency of a variable is not observed.
- All date values will be presented as YYYY-MM-DD (e.g., 2013-05-17) ISO 8601 format.
- All observed time values will be presented using a 24-hour clock HH:MM:SS format (e.g., 01:35:45 or 11:26). Seconds should only be reported if they were measured as part of the trial, also in ISO 8601 format.
- Time durations will be reported in mixed HHh MMm SSs notation (e.g., 5h 32m, or 27h 52m 31s). The use of decimal notation to present (display) time durations should be avoided (e.g., 0.083h = 5m) unless it is necessary to show the computation of time differences in a table, figure, or data listing, in which case both notations may be used to display the time duration.
- All tables, figures, and data listings will have the Table, Listing, or Figure status (DRAFT, FINAL) at the top of each output, and a date/time stamp on the bottom of each output.
- All analysis programs developed for a table, figure, or data listing display will be self-contained to facilitate transfer of programs to multiple computing environments and transfer to a regulatory agency (if requested).

